### **6.10.3 Blood Analyses**

Fasting ( $\geq 8$  hours) blood (approximately 2 tablespoons) will be collected for the measurement of lipids (total-, LDL-, HDL-cholesterol, and triglycerides), glucose, and insulin (to be assayed in Fairview Diagnostics Laboratories, Fairview-University Medical Center, Minneapolis, MN - a Center for Disease Control and Prevention certified laboratory). Fasting samples for C-reactive protein and oxidized LDL cholesterol will be processed and stored at -80 degrees C for a batched analysis in the University of Minnesota Cytokine Reference Laboratory (CLIA licensed).

### **6.10.4 Lifestyle/Behavioral Modification Counseling**

All participants, regardless of group assignment, will receive the same lifestyle/behavioral modification counseling monthly throughout the entire study: delivered at each in-person study visit and on the phone for months when there is no study visit. The lifestyle/behavioral modification curriculum has been adapted from the NIDDK-sponsored TODAY study lifestyle modification program materials and utilized by our group in a previous and ongoing trial. Trained study coordinators will deliver the lifestyle/behavioral modification counseling, which will focus on small, successive changes in dietary (after meal replacement induction period) and physical activity behaviors through the use of evidence-based behavior change strategies such as self-monitoring, goal setting, reinforcement for goal achievement, stimulus control, social support, problem solving, and motivational techniques. The educational materials will be given to subjects and parents at the first study visit and selected sections will be reviewed and discussed at each face-to-face and phone-based lifestyle modification counseling session. We have previously demonstrated the effectiveness of this lifestyle modification protocol in a randomized, placebo-controlled trial among adolescents with severe obesity. The intensity of the lifestyle modification is designed to be practical and feasible in the clinic setting.

### **6.10.5 Meal Replacement Therapy**

All participants, regardless of assignment to the financial incentives group or control group, will engage in meal replacement therapy throughout the entire 52-week trial. Participants will be asked to strictly follow the prescribed eating regimen, which will include provision (home delivery) of pre-packaged meals from Healthy for Life (1,200 kcals per day). Meals will be provided free of charge. Guidance will be provided regarding the use of the meals at school, and participants will be encouraged to engage in family meal sessions despite eating different foods.

### **6.10.6 Financial Incentives**

With the intent of utilizing a straight-forward process with clear goals for the participants, financial incentives will be tied to individual percent reduction in body weight (changes in

CONFIDENTIAL

This material is the property of the University of Minnesota. Do not disclose or use except as authorized in writing by the study sponsor

body weight and BMI can differ slightly based on growth but are highly correlated). We believe the complexity of basing incentives on BMI reduction would create confusion and frustration for the participants owing to the interplay between changes in height and weight ultimately making it difficult to effectively communicate goals to the participants. Moreover, change in height is obviously beyond the domain of control for participants and offering higher payouts to individuals who experience greater increases in height will be viewed as unfair. Using the baseline body weight as the reference for all subsequent study visits (to avoid offering incentives for weight cycling – gain and subsequent loss), participants will receive \$20 (in the form of a gift card) for every 0.5% reduction in body weight from baseline. To make goals clear for participants, individual tables will be created displaying the amount of weight loss (in pounds) corresponding to each half percentage-point reduction in body weight. Financial incentive payments, if earned, will be made to participants in the financial incentives group at all study visits. Even if unsuccessful in earning a payment at a preceding visit, participants will remain eligible for the incentives at all subsequent visits (i.e., if weight is gained or remains stable, participants will have the opportunity to get back on track; again, in relation to the baseline body weight). No payment will be made for partial goal attainment (i.e., full 0.5% weight reduction increments must be achieved).

#### **6.10.7 Assessment of Motivation, and Other Behavioral and Psychosocial Factors**

Questionnaires to be utilized at the same time points will measure quality of life (PedsQL Child and Parent questionnaire; Impact of Weight on Quality of Life: IWQOL-Kids), anxiety (Screen for Child Anxiety Related Disorders: SCARED questionnaire) and depression (Depression Scale for Children: CES-DC questionnaire). Weight reduction will be measured at all study visits.

#### **6.10.8 Vascular Measurements**

Vascular testing will be performed in the morning in a quiet room of constant temperature (22° C – 23° C). Participants will be fasting and will be instructed to refrain from caffeine and medications prior to the study.

Carotid-radial, carotid-femoral, and/or carotid-foot augmentation index and pulse wave velocity will be measured by the SphygmoCor® MM3 system (AtCor Medical, Sydney, Australia). Augmentation index is a measure of the relative magnitude of the reflected (or retrograde) pulse wave early in the cardiac cycle. Higher values represent increased arterial stiffening. Pulse wave velocity will be calculated as distance divided by transit time. Higher values of pulse wave velocity represent increased arterial stiffness.

Resting heart rate variability will be measured with the SphygmoCor® MM3 system.

### **7 Statistical Plan**

#### **7.1 Participant Populations for Analysis**

The primary analysis will be on an intent-to-treat population where all randomized participants will be evaluated according to their treatment assignment (financial incentives vs. no financial incentives). The analysis will be conducted with multiple imputation techniques, if necessary. A secondary per protocol analysis will include participants who are without major protocol violations. Safety assessments will include all participants who receive any treatment according to the treatment they receive. Randomization will be stratified by health insurance status

CONFIDENTIAL

This material is the property of the University of Minnesota. Do not disclose or use except as authorized in writing by the study sponsor

(public/Medicaid vs. private), which is highly-quantifiable, clinically-relevant, and closely associated with family income and socioeconomic status.

- Intent-to-treat (ITT): All participants randomized according to the treatment assignment received.
- Per-Protocol (PP): All participants randomized without major protocol violations and who were compliant (at least 80%) with the treatment assignment received. Major protocol violations include: cessation of study meals.
- Safety Population: All participants who receive any amount of treatment according to the treatment they receive.

## 7.2 Sample Size Determination

Based on results of adult clinical trials of financial incentives for weight loss, we anticipate a control-subtracted treatment effect (BMI reduction, our primary endpoint) of 5% at 52 weeks. We estimate having a dropout rate of no more than 20% (our previous clinical trial experience with this population has been 10-15%). We do not expect to observe differential attrition by treatment arm based on results of adult financial incentives trials demonstrating nearly identical study completion rates among the control and treatment groups. Using BMI variability estimates from a previous trial using meal replacements over 12 months suggesting a standard deviation of approximately 8.8 and using a conservative correlation between baseline and follow-up scores of 0.6, we present in Table 2 the power associated with a clinically-meaningful control-subtracted BMI reduction of 5% based on an overall sample size of 130 (60 in each treatment arm) and a range of degrees of attrition (including rows reflecting scenarios of higher than expected levels).

**Table 2. Conservative Estimates of Power for a Range of Potential Treatment Effects at 52 Weeks**

Difference in BMI Percent Change	5%
Two-sided Unadjusted	97.18%
Two-sided with 10% attrition	95.67%
Two-sided with 15% attrition	94.5%
Two-sided with 20% attrition	93.25%

## 7.3 Statistical Methods

Descriptive analyses of baseline characteristics and outcomes will include means and standard deviations for continuous variables and frequencies for categorical variables. Treatment compliance will also be evaluated. Safety analyses will use the Safety analysis population and will be primarily descriptive, reporting the number and percentage of adverse events.

### 7.3.1 Specific Aim #1 (Primary and Secondary Endpoints)

The primary analysis will be conducted using the intent-to-treat population to compare the mean BMI percent change from randomization to 52 weeks (additional analyses will use the 26-week time-point as secondary) of follow-up between the financial incentives and no financial incentives groups, adjusted for BMI at randomization and insurance status (randomization stratification factor) for added precision. Confidence intervals (CIs) and P-values will be based on robust variance estimation. Statistical significance will be considered as  $p < 0.05$ . Supportive analyses using the per-protocol population will

CONFIDENTIAL

This material is the property of the University of Minnesota. Do not disclose or use except as authorized in writing by the study sponsor

also be conducted along with consideration of adjustment for residual imbalances between treatment groups after randomization (e.g., in sex).

Secondary endpoints of body fat (total, visceral, and subcutaneous), blood pressure, triglycerides/HDL ratio, inflammation, oxidative stress, arterial stiffness, heart rate variability, and adherence to the meal replacement regimen will be characterized at 26 and 52 weeks. The evaluation will be in a similar fashion as the primary outcome wherein analyses will be adjusted for baseline values and the randomization stratification factor. Longitudinal analyses will also be conducted, incorporating the variables that are measured at multiple time points (e.g., blood pressure, adherence). Supportive analyses using the PP population will also be conducted. We also recognize there is always the possibility of subgroups with differential treatment effect. We do not a priori have a particular subgroup of interest the study is designed to evaluate, though exploratory analyses would be able to investigate such.

### 7.3.2 Specific Aim #2

We will explore cut-offs of percent change in BMI from randomization that are associated with significant improvement in cardiometabolic risk factors and vascular health. We anticipate a range of values for consideration as the cut-off across the two treatment groups. We also anticipate the cut-off not necessarily being the same across different endpoints. The analyses will be similar to those for continuous outcomes outlined above with adjustment for baseline values, but groups will be determined by candidate cut-offs rather than treatment assignment. This will also allow for quantifying the degree of normalization within each subgroup with point estimates and confidence intervals and also for comparing the post-intervention values against the distribution of values from the existing control database (normal weight, overweight, and obese groups).

Other scales will also be explored, e.g., absolute BMI, percent of the 95th BMI percentile, BMI z-score, total body fat, percent body fat, total visceral fat, and percent visceral fat at follow-up, in addition to percent change in BMI from randomization. Results of these analyses will be considered exploratory, interpreted as suggestive, requiring confirmation. It is also possible thresholds may differ for different types of participants, e.g., based on sex. Such interactions will be explored to the extent there are sufficient numbers of individuals within subgroups and sufficient variability over which to explore thresholds. In addition, these results will be used to aid in the interpretation of the clinical meaningfulness of the treatment effect from aim #1. For example, if a cutoff of 4% BMI reduction is associated with clinically meaningful improvements in at least some of the cardiometabolic risk factors, we will examine how many participants met this threshold in each group. In an exploratory fashion, we will utilize the receiver operating characteristic (ROC) analysis to describe the sensitivity and specificity of various BMI reductions cut-points associated with remission of dichotomous co-morbidities at baseline such as dyslipidemia, pre-hypertension/hypertension, pre-diabetes, etc. (in the subset of participants with these conditions at baseline).

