Therefore, in the current study, we will conduct a clinical trial to determine whether meal replacement therapy plus financial incentives leads to superior weight loss and better health outcomes among adolescents with severe obesity and we will identify the various thresholds of weight loss necessary to achieve specific cardiometabolic risk factor, co-morbidity, and vascular improvements in this unique patient population. Moreover, we will also be able to describe the degree of normalization of cardiometabolic risk factors and vascular outcomes according to varying amounts of weight reduction and compare (in a cross-sectional fashion) post-intervention values to an existing database of youth with normal weight, overweight, and obesity tested in the same facilities/laboratory using the same protocol and methods. Beyond body weight/BMI loss, we will also be able to identify thresholds of reduction in absolute and percent total body fat and absolute and percent visceral fat that are associated with improvements in cardiometabolic risk factors and vascular health.

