Our second study aim will address an equally significant and highly-relevant unanswered question regarding the treatment of pediatric patients with severe obesity. We will describe for the first time, the thresholds of weight loss required to elicit clinically-meaningful improvements in specific cardiometabolic risk factors and measures of vascular health among youth with severe obesity. Pediatricians need evidence regarding the amount of weight loss they should strive to achieve for their pediatric patients with severe obesity since it will inform the type and intensity of the treatment approach. Although evidence-based benchmarks have been established for adults, no such thresholds have been identified in youth with severe obesity. Owing to the distinct physiological, psychosocial, and demographic features of pediatric severe obesity, it would be inappropriate to assume that the thresholds of weight loss shown to be important for adults also apply to this unique patient population. Therefore, the new knowledge generated from our study will serve as a meaningful advancement in the field of pediatric obesity medicine as it will inform the treatment approach for individual patients and provide an evidence base from which to begin to develop clinical practice guidelines.

The following studies provide the background and rationale for our plans to move forward. Our project is a logical extension of this foundational work, which has informed the basis of the trial detailed in this protocol.

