**Figure 1. Weight Loss with Meal Replacement Therapy in Adolescents with Severe Obesity**

We are currently conducting a clinical trial that includes a 4-week meal replacement induction period (prior to randomization to topiramate or placebo) and have observed promising BMI reduction in adolescents with severe obesity (N=19). Mean BMI reduction was 3.2% in only four weeks (Figure 1). These data are consistent with the findings of Berkowitz and colleagues and demonstrate the feasibility of meal replacement therapy in our hands.

Anecdotally, our participants have had a very positive experience with the meal

replacement program and reported high levels of satisfaction with the degree of weight reduction in such a short period of time and with the convenience of the treatment regimen.

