#### *Weight Loss Thresholds and Cardiometabolic Risk Factor Improvements in Adolescents with Severe Obesity*

[figure not shown]
Using data from the 19 participants who have completed the 1-month meal replacement period (prior to randomization to drug or placebo) in our ongoing previously-mentioned clinical trial, we compared cardiometabolic risk factor outcomes between those achieving  $\geq 4\%$  (N=7) vs.  $< 4\%$  (N=12) BMI reduction (Figure 2). Note: comparisons of thresholds of 1%, 2%, and 3% BMI reduction did not yield either statistically-significant or clinically-meaningful improvements in risk factors at these lower levels of weight loss. Although a much larger sample size will be required to sufficiently identify important and relevant thresholds of BMI reduction, these preliminary data suggest that 4% BMI reduction elicits significant and clinically-meaningful improvements in multiple cardiometabolic risk factors among teens with severe obesity (>10% improvements in many of the risk factors).

CONFIDENTIAL

This material is the property of the University of Minnesota. Do not disclose or use except as authorized in writing by the study sponsor

In the context of the much larger proposed study, we will have the flexibility to compare a wide range of BMI reduction thresholds and identify the cutoffs most closely associated with specific cardiometabolic risk factors improvements. Our findings will have an immediate and sustained clinical impact by providing pediatric weight management specialists with critical information regarding weight loss goals for their patients with severe obesity. Beyond body weight/BMI loss, we will also be able to identify thresholds of reduction in absolute and percent total body fat and absolute and percent visceral fat that are associated with improvements in cardiometabolic risk factors and vascular health. Our group has done some of the pioneering work validating the innovative use of iDXA technology to quantify visceral fat in youth.

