### 2.2 Secondary Objectives

Identify weight loss thresholds associated with significant improvements in cardiometabolic risk factors and vascular health in adolescents with severe obesity. We hypothesize that a minimum weight loss threshold exists, that when exceeded, will be associated with meaningful improvements in multiple cardiometabolic risk factors and parameters of vascular health.

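### A significant weight-loss cut-off in Aim 2 would not by itself show the hypothesised threshold, because no planned analysis compares a threshold with a graded relation

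*Combined protocol and SAP*

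**What the plan says.** Section 2.2 makes the threshold a hypothesis: "We hypothesize that a minimum weight loss threshold exists, that when exceeded, will be associated with meaningful improvements". Section 1.2 (Significance and Preliminary Work) promises to describe "the thresholds of weight loss required to elicit clinically-meaningful improvements in specific cardiometabolic risk factors".

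The analysis is in section 7.3.2, with the same core text in section 3.2. It is a baseline-adjusted comparison like that for the continuous outcomes, except that "groups will be determined by candidate cut-offs rather than treatment assignment". Cut-offs are of interest when associated with significant improvement, and section 1.2 adds the aim to "identify the cutoffs most closely associated with specific cardiometabolic risk factors improvements". The plan does not list the cut-offs. It also does not say whether groups are above/below splits or bands. The pilot in section 1.2 used an above/below split at 4%, while section 1.1 speaks of being able to "describe the degree of normalization of cardiometabolic risk factors and vascular outcomes according to varying amounts of weight reduction", which would fit bands.

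Section 7.3.2 also contains subgroup estimates with confidence intervals, a comparison with an existing control database, and an ROC analysis for remission of conditions present at baseline. It calls results exploratory and in need of confirmation. It would also use a cut-off (4% is the example) to help interpret the Aim 1 effect, by counting participants in each arm who reached it. No regression on continuous loss and no test of a step against a line is described.

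**The concern.** If a risk factor improves steadily with each point of BMI lost, any cut-off divides participants into a group that lost a lot and a group that lost little. The two will differ, and with enough data the difference will be significant at almost any cut-off. The same happens if a true step exists. Significance at a cut-off shows that loss and improvement are associated. It does not show that there is a minimum loss below which nothing happens, which is what section 2.2 hypothesises.

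A second point concerns how group results are reported. If groups are above/below splits, the upper group contains everyone from just over the cut-off to the largest losers. Its mean improvement belongs to its mean loss, not to the cut-off.

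At stake is the answer to the stated secondary objective, and any cut-off carried over to judge the clinical meaning of Aim 1.

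**Working it through.** **Inputs from the plan (section 7.2).** SD 8.8, baseline to follow-up correlation 0.6, arm difference 5 points, dropout at most 20%. Baseline-adjusted SD: 8.8 × √(1 − 0.6²) = 7.04. As a check on this reading, 5 points with SD 7.04 and 60 per arm gives power of 97.1% (t) or 97.3% (normal), against 97.18% in Table 2. Completers: 0.8 × 130 = 104. The documents give no operating characteristics for Aim 2.

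**Assumed, not in the documents.** Normal losses with SD 7.04 within arm, arm means 2.5% and 7.5%, cut-offs 1, 2, 3, 4, 5, 6, 8 and 10%, above/below groups, correlation r of loss with improvement 0.2 to 0.4.

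**Step 1: what a cut-off contrasts.** For an arm with mean μ, the proportion above c is p = 1 − Φ((c − μ)/7.04), and its contribution to total loss is μp + 7.04 φ((c − μ)/7.04). At c = 4:
- Mean 2.5: p = 0.416, contribution 2.5 × 0.416 + 7.04 × 0.390 = 3.79.
- Mean 7.5: p = 0.690, contribution 7.5 × 0.690 + 7.04 × 0.353 = 7.66.
- Mean loss above 4%: (3.79 + 7.66)/(0.416 + 0.690) = 10.35%.
- Mean loss below 4%: (10 − 11.45)/(2 − 1.106) = −1.6%, a small gain.

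The gap is about 12.0 points. Over the eight cut-offs it is 11.9 to 12.7, so under a line every cut-off contrasts nearly the same difference in loss.

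**Step 2: how often a cut-off is significant.** Simulated trials, 52 per arm; above/below indicator adjusted for the baseline value and insurance status, robust variance, p<0.05:

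| | r=0.2 | r=0.3 | r=0.4 |
|---|---|---|---|
| Any cut-off significant, line | 62-64% | 91% | 98-99% |
| Any cut-off significant, step at 5% | 66% | 92% | 99% or more |
| Smallest p at 5%, line | 9% | 10% | 12% |
| Smallest p at 5%, step at 5% | 31% | 44% | 60% |

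With no relation at all, some cut-off is significant in 17% of trials. A separate simulation with ten cut-offs and a control mean of 2% gave 67-69%, 91-92% and 99% under a line, and 66-70%, 93-94% and nearly 100% under a step.

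**Step 3: improvement at a 4% loss, r = 0.3, line through zero.** The SD of loss over both arms is √(7.04² + 2.5²) = 7.47. The slope is 0.3/7.47 = 0.040 SD per point. The true improvement at 4% is 4 × 0.3/7.47 = 0.16 SD. The above-4% group shows 10.35 × 0.3/7.47 = 0.42 SD. A band from 4% to under 8% has mean loss 6.0% and shows 0.24 SD, but holds about 22 of 104 participants (sampling SD 0.21). A continuous model gives 0.16 SD (sampling SD 0.10).

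**Step 4: the same comparison if the truth is a step at 5%, r = 0.3.** Half the participants are above 5%, so the step is 0.3/0.5 = 0.60 SD. The mean loss above 5% is 10.97%, so the fitted slope is 0.60 × 0.5 × (10.97 − 5)/7.47² = 0.032. The line then credits 0.30 − 0.032 = 0.27 SD at 4%, where the truth is 0, and 0.30 + 3 × 0.032 = 0.40 SD at 8%, where the truth is 0.60. The above-5% group recovers 0.60.

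**Step 5: a direct step check.** Adding a step to the linear model and scanning eight cut-offs needs a critical |t| of about 2.70. Using 1.98 signals a step in 23% of trials under a true line. At 2.70, power for a step at 5% is 27% (r = 0.3) and 53% (r = 0.4). The ten-cut-off simulation gave 35% and 63%.

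**The case against.** The strongest reply has five parts.

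- **The objective is about exceeding a cut-off.** Section 2.2 speaks of improvement once a threshold is exceeded, and the Aim 1 use counts participants who reached it. The mean of those above a cut-off is a legitimate answer to that. This stands. A reader might infer that the plan will report the above-4% mean as the effect of a 4% loss, but section 7.3.2 does not say so. The pilot comes close, with "these preliminary data suggest that 4% BMI reduction elicits significant and clinically-meaningful improvements in multiple cardiometabolic risk factors" after noting that "comparisons of thresholds of 1%, 2%, and 3% BMI reduction did not yield either statistically-significant or clinically-meaningful improvements in risk factors". That is background, resting on both statistical and clinical grounds and followed by a call for a much larger sample. It shows a reading to guard against, not the planned analysis.
- **The grouping is unstated.** This also stands. Step 3's larger figure applies only to above/below groups, and bands reduce the bias at the cost of precision.
- **The scan carries information.** It does: the smallest p falls at the true step clearly more often than chance placement under a line. It would be wrong to infer that the cut-off comparison is uninformative. What is missing is a stated rule for using it.
- **A linear model is no better under the protocol's own hypothesis.** Step 4 confirms this. A reader might infer that the linear model should replace the cut-off groups; the figures do not support that.
- **The aim is exploratory.** I read that label as covering the whole aim. It limits how strongly a result is stated, but a significant cut-off still does not distinguish the two shapes.

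**Conclusion.** The point holds in a limited form. As written, Aim 2 has no analysis that compares a threshold with a graded relation. In the settings examined, a significant cut-off appears about equally often under either, with differences of a few points at most. It should not be read as support for the hypothesis in section 2.2.

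The second part is conditional. If groups are above/below splits, those above 4% lose about 10% on average (8.0% to 11.9% for SD 5 to 8.8 and arm means from 0/5 to 3/8), so their mean improvement should not be presented as that expected at a 4% loss.

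The rates depend on the assumed correlation, arm means and cut-offs. The near-constant gap depends on normality: with skewed, exponential-shaped residuals it runs from 9.8 to 14.9 points. The conclusion that significance does not separate line from step does not need the gap to be constant. Severity is low to moderate: the aim is exploratory and the primary endpoint is untouched.

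**What to change.** In sections 7.3.2 and 3.2, keep the cut-off groups and ROC analysis and add the following:

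1. For each risk factor, model its change on continuous percent BMI change, adjusted for the baseline value and insurance status, with the robust variance already planned. Show the fitted curve with its confidence interval.
2. Claim a threshold only if a step or segmented term improves on the linear fit after allowing for the search over cut-offs. Do not read a non-significant test as proof of linearity.
3. State how groups are formed and report the mean loss within each group.
4. Label any data-derived cut-off used to interpret Aim 1 as data-derived.

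Stating a meaningful improvement for each continuous risk factor, and reporting the loss at which the curve reaches it, would be useful but is optional. The interval would be wide: for a 0.3 SD improvement at r = 0.3 under a line, the true target is 7.5% and the median 95% CI runs from 2.0% to 15.9%.

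The cost is plan wording and modest extra analysis of data already being collected. The step check has low power (Step 5), so many trials would end without a clear answer on shape. Because a line misleads when the truth is a step, and a cut-off contrast misleads when the truth is a line, neither should be reported alone.
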